### 6.3.1.2. AEs by System Organ Class and Preferred Term

The following summary tables of AE newly occurred after study vaccination or any AE already present that worsens after exposure to study vaccination will be provided by MedDRA SOC and PT using frequency, counts, and percentages (i.e., number and percentage of participants with an event):

- All unsolicited AEs up to 28 days after injection
- All unsolicited treatment-related AEs up to 28 days after injection and up to EoS throughout the study
- All unsolicited AE up to 28 Days After Injection with Occurrence in  $\geq 1\%$  of Participants in Any Vaccination Group
- All serious AEs up to 28 days after injection and up to EoS throughout the study
- All serious AEs that are treatment-related up to 28 days after injection and up to EoS throughout the study
- All unsolicited AEs leading to discontinuation from participation in the study up to 28 days after injection and up to EoS throughout the study
- All unsolicited severe AEs up to 28 days after injection
- All unsolicited severe AEs that are treatment-related up to 28 days after injection
- All unsolicited medically attended AEs up to 28 days after injection and up to EoS throughout the study
- All unsolicited medically attended AEs that are treatment-related up to 28 days after injection and up to EoS throughout the study
- All AESIs up to 28 days after injection and up to EoS throughout the study
- All non-serious AEs up to 28 days after injection
- All non-serious severe AEs up to 28 days after injection

### 6.3.1.3. AEs by Preferred Term

A summary table by PT will be provided for all unsolicited AEs newly occurred after study vaccination or any AE already present that worsens after exposure to study vaccination up to 28 days after injection. AEs with fatal outcome up to 28 days after injection and up to EoS throughout the study will also be summarized by PT.

PTs will be sorted in a descending order according to the frequency in the overall group.

#### **6.3.1.4. AEs by System Organ Class, Preferred Term and Severity**

The following summary tables will be provided for all unsolicited AEs newly occurred after study vaccination or any AE already present that worsens after exposure to study vaccination up to 28 days after injection by SOC, PT, and maximum severity using frequency counts and percentages:

- All unsolicited AEs
- All unsolicited AEs that are treatment-related

#### **6.3.1.5. Selected AEs of Clinical Interests by SMQ and Preferred Term**

The number of participants with occurrences of selected AEs of clinical interests identified by SMQ up to 28 days and up to EoS throughout the study will be summarized, respectively. Only AEs newly occurred after study vaccination or any AE already present that worsens after exposure to study vaccination will be summarized. SMQ will be summarized by PT, if applicable. Detailed description of SMQ is presented in [Appendix G Table 5](#) and [Table 6](#). Additional SMQs may be summarized, as necessary.

In addition, the number of participants with anaphylactic reaction up to 28 days and up to EoS throughout the study is summarized by vaccination groups, respectively.

#### **6.3.1.6. Independent Cardiac Event Adjudication Committee**

An independent CEAC of medically qualified personnel, including cardiologists, will review suspected cases of myocarditis and pericarditis to determine if they meet CDC criteria of “probable” or “confirmed” events, and to assess severity (see more details in the protocol Section 10.1.6.2) and provide the assessment to the Sponsor. The CEAC members will be blinded to study treatment. Details regarding the CEAC composition, responsibilities, procedures, and frequency of data review can be found in the CEAC charter.

CEAC will be presented in a listing.

#### **6.3.2. Solicited Adverse Reactions**

An AR is any AE for which there is a reasonable possibility that the test product caused the AE. The term “Solicited Adverse Reactions” refers to selected signs and symptoms occurring after injection administration during a specified post-injection follow-up period

(day of injection and 6 subsequent days). The solicited ARs are recorded by the participant in eDiary. The occurrence and intensity of selected signs and symptoms is actively solicited from the participant during a specified post-injection follow-up period (day of injection and 6 subsequent days), using a pre-defined checklist in the eDiary (i.e., solicited ARs). Any solicited ARs occurring within 7 days after injection, if not entered in the eDiary in the required input time window, should be reported in the Reactogenicity eCRF. Solicited ARs reported in both the eCRF and eDiary will be included in the evaluation of solicited ARs.

The following local ARs will be solicited: pain at injection site, erythema (redness) at injection site, swelling/induration (hardness) at injection site, and axillary (underarm) swelling or tenderness ipsilateral to the side of injection.

The following systemic ARs will be solicited: headache, fatigue, myalgia (muscle aches all over the body), arthralgia (joint aches in several joints), nausea/vomiting, chills, and fever.

The solicited ARs will be graded based on the grading scales presented in Table 7 in the protocol, modified from the Toxicity Grading Scale for Healthy Adult and Adolescent Volunteers Enrolled in Preventative Vaccine Clinical Trials ([DHHS 2007](#)). Investigator will assess Grade 4 events (with exception of fever).

If a participant reports a solicited AR with onset during the solicited period, but they did not record the event in the eDiary, then the event should be recorded by study staff in the EDC where reactogenicity is collected.

If a solicited local or systemic AR continues beyond 7 days post injection, the participant should notify the site to provide an end date and close out the event in the EDC where reactogenicity is collected.

All solicited ARs (local and systemic) will be considered causally related to injection.

All solicited ARs analyses will be based on Solicited Safety Set and will be provided by treatment group, unless otherwise specified.

An overall summary of solicited ARs including the number and percentage of participants who reported any solicited AR, any solicited local AR, and any solicited systemic AR within 30 minutes and 7 days after injection, grade 3 or grade 4 Solicited AR will be summarized.

The number and percentage of participants who reported any solicited AR, any solicited local AR, and any systemic solicited AR within 7 days after injection will be tabulated with a two-sided 95% exact confidence interval (CI) using the Clopper-Pearson method.

The number and percentage of participants who reported any solicited AR, any solicited local AR, any systemic solicited AR and individual solicited ARs (has a severity grade of Grade 1 or greater) within 7 days after injection will be tabulated and plotted by severity grade. Participants are counted under the maximum severity grade within each event.

The number and percentage of participants experiencing fever (a temperature greater than or equal to 38.0°C/100.4°F by the oral, axillary, or tympanic route) by severity grade will be provided. Participants are counted under the maximum severity grade within each event.

The onset day of an individual solicited AR is defined as the time point at which the solicited AR first occurred. The number and percentage of participants who reported any solicited AR, any solicited local AR, systemic solicited AR and individual solicited ARs (has a severity grade of Grade 1 or greater) within 7 days after injection will be summarized by onset day.

The duration (days) of each solicited AR will be summarized. Duration will be calculated as end date of solicited AR – onset date of solicited AR + 1, no matter if it is intermittent or continued or if the solicited AR continues beyond 7 days.

All solicited ARs that continue beyond 7 days after injection will be summarized and presented in separate data listings.

### **6.3.3. Clinical Laboratory Evaluations**

The pregnancy testing results using highly sensitive serum or urine hCG will be performed as needed for person of childbearing potential, and follicle stimulating hormone and estradiol tests will be performed as needed for person of nonchildbearing potential. These results will be listed.

### **6.3.4. Vital Sign Measurements**

Vital sign measurements, including systolic and diastolic blood pressures, pulse, respiratory rate, and temperature, will be presented in a data listing.

Observed values and changes from baseline for all vital sign measurements will be summarized at each scheduled visit by the treatment groups. Vital sign measurements will

also be summarized using a shift grading table from pre-dose to post-dose by vaccination group according to the toxicity grading criteria in [Appendix H](#).

## 6.4. Immunogenicity Analysis

The analysis of immunogenicity will be analyzed by vaccination group based on the PPS. If the number of participants in the FAS and PPS differ (defined as the difference divided by the total number of participants in the PPS by more than 10%), supportive analyses of immunogenicity may be conducted using the FAS. Supportive analysis is required if the condition is met at end of study; it is optional for the IA.

### 6.4.1. Immunogenicity Assessments

There will be two types of immunogenicity assessments:

- Vaccine-specific humoral immune responses, including serum antibody levels as measured by the HAI assay. Additional vaccine-specific humoral immune response assessments may include analysis of neutralizing antibody titers, antibody functionality, epitope specificity, and affinity.
- CCI  
[REDACTED]  
[REDACTED]  
[REDACTED]  
[REDACTED]  
[REDACTED]

### 6.4.2. Analysis of Humoral Immunogenicity Endpoints

Immunogenicity assessments of serum antibody levels as measured by HAI assay at CCI  
[REDACTED] will be included in the analyses below.

Data collected following intercurrent events ([Section 6.4.3](#)) will not be included in data summaries or inferential analyses described in this section.

#### 6.4.2.1 Geometric Mean Titer and Geometric Mean Fold Rise

- The following immunogenicity endpoints will be evaluated: Geometric mean titer (GMT) at indicated timepoints as measured by HAI assay.
- Geometric mean fold rise (GMFR), comparing each timepoint with D1 (Baseline) as measured by HAI assay.

The GMT will be calculated using the following formula:

$$2^{\left\{ \frac{\sum_{i=1}^n \log_2(t_i)}{n} \right\}}$$

where  $t_1, t_2, \dots, t_n$  are  $n$  observed immunogenicity titers.

The GMFR measures the changes in immunogenicity titers within participants. The GMFR will be calculated using the following formula:

$$2^{\left\{ \frac{\sum_{i=1}^n \log_2(v_{ij}/v_{ik})}{n} \right\}} = 2^{\left\{ \frac{\sum_{i=1}^n \log_2(v_{ij}) - \log_2(v_{ik})}{n} \right\}}$$

where, for  $n$  participants,  $v_{ij}$  and  $v_{ik}$  are observed immunogenicity titers for participant  $i$  at time points  $j$  and  $k$ ,  $j \neq k$  and  $k$  is baseline. The 95% CIs for GMT and GMFR will be calculated based on the t distribution of the log-transformed values and then back transformed to the original scale for presentation.

- The following evaluations will be performed at baseline (Day 1) and each post-baseline time point: GMT of antibody levels with corresponding 95% CI will be provided at CCI [REDACTED]. GMTs with 95% CI will be plotted at each time point. The following descriptive statistics will also be provided at CCI [REDACTED] the number of participants (n), median, minimum, and maximum.
- GMFR of antibody levels with corresponding 95% CI will be provided at CCI [REDACTED] over pre-injection at (Day 1 [baseline]). GMFRs and corresponding 95% CI will be plotted at each post-baseline time point.

#### 6.4.2.2 Comparisons between mRNA-1010 and Comparator Groups

CCI [REDACTED]  
 [REDACTED]  
 [REDACTED]  
 [REDACTED]

CCI

### 6.4.2.3 Seroresponse

The immunogenicity endpoint of seroresponse is defined as the proportion of participants with an increase of antibody titers and concentrations from baseline below the LLOQ to  $\geq 4 \times$  LLOQ, or at least a 4-fold rise from baseline if baseline is  $\geq$  LLOQ.

- The number and percentage of participants with seroresponse from Day 1 (baseline) to CCI [REDACTED] will be provided with 2-sided 95% CI using the Clopper-

Pearson method. Seroresponse rate and corresponding 95% CI will be plotted at each post-baseline time point.

- CCI [REDACTED]
- [REDACTED]
- [REDACTED]
- [REDACTED]
- [REDACTED]
- [REDACTED]
- [REDACTED]

#### **6.4.2.4 Proportion of participants with HAI titer $\geq 1:40$**

The number and percentage of participants with a HAI titer  $\geq 1:40$  at CCI [REDACTED] will be provided with 2-sided 95% CI using the Clopper-Pearson method.

CCI [REDACTED]

[REDACTED]

[REDACTED]

[REDACTED]

[REDACTED]

[REDACTED]

#### **6.4.3. Handling of Intercurrent Events**

Intercurrent events are events occurring after treatment initiation that affect either the interpretation or the existence of the measurements associated with the clinical question of interest.

The potential intercurrent events for this study are listed in [Table 3](#).

**Table 3: Intercurrent Events**

Intercurrent Event	Identification Method
Intercurrent infections	
Captured from RTPCR, and from the adverse events (AE) page through a manual review based on dictionary-derived terms (preferred terms).
 
Immunogenicity data collected after the first occurrence of intercurrent infections will be excluded (censored) from analysis.

Use of prohibited medication or non-study vaccines	
Collected on the concomitant therapies case report form or protocol deviation form. Non-study vaccines only include vaccines against influenza.
 
Subject will be excluded from PPS.

Visit window important deviations	
Collected from protocol deviation form
 
Subject will be excluded from PPS.

#### 6.4.4. Subgroup Analyses

No subgroup analyses are planned for the study.

#### 6.4.5. Nasopharyngeal Swab for Virus Detection

Nasopharyngeal swab for virus detection and available results will be listed.

#### 6.5. Planned Analyses

CCI

**CCI**

The final CSR will include full unblinded analyses of all safety and immunogenicity with individual unblinded listings through EoS.

## **7. Changes from Planned Study Design and Analyses in Protocol**

Randomization will not be stratified by Receipt of a 2022-2023 NH influenza vaccine (Yes/No). No stratification factor will be used in this study.

For immunogenicity analysis, the number and percentage of participants with >2-, 3-fold increases from Baseline (if  $\geq$ LLOQ) or with >2-, 3-fold increases from LLOQ (if <LLOQ) will not be analyzed with 2-sided 95% CI per Protocol.

## 9. List of Appendices

### 9.1. Appendix A Standards for Safety and Immunogenicity Variable Display in TFLs

**Continuous Variables:** The precision for continuous variables will be based on the precision of the data itself. The mean, median, Q1 and Q3 will be presented to one decimal place more than the original results; the SD will be presented to two decimal places more than the original results; the minimum and maximum will be presented to the same precision as the original results.

**Categorical Variables:** Percentages will be presented to 1 decimal place.

## 9.2. Appendix B Analysis Visit Windows for Safety and Immunogenicity Analysis

Safety and Immunogenicity Analysis will be summarized using the following analysis visit window for post injection assessments:

Step 1: If the assessments are collected at a scheduled visit, the collected data will be mapped to the nominal scheduled visit.

Step 2: If the assessments are collected at an unscheduled visit, the collected data will be mapped using the analysis visit windows described in [Table 4](#) below.

If a participant has multiple assessments within the same analysis visit, the following rule will be used:

- If multiple assessments occur within both scheduled visit and unscheduled visit, the assessment collected at scheduled visit will be used.
- If multiple assessments occur within a given analysis visit, the assessment closest to the target study day will be used.
- If there are 2 or more assessments with equal distance to the target study day, the last assessment will be used.

Visit	Target Study Day	Visit Window in Study Day
CCI		

### 9.3. Appendix C Imputation Rules for Missing Dates of Prior/Concomitant Medications

Imputation rules for missing or partial medication start/stop dates are defined below:

1. Missing or partial medication start date:

- If only Day is missing, use the first day of the month, unless:
  - The medication end date is after the date of injection or is missing AND the start month and year of the medication coincide with the start month and year of injection AND the medication is not known to be taken prior to study administration (e.g. answer to the question of “Was the medication taken prior to study administration?” in CRF is not Yes). In this case, use the date of injection.
- If Day and Month are both missing, use the first day of the year, unless:
  - The medication end date is after the date of injection or is missing AND the start year of the medication coincides with the start year of injection AND the medication is not known to be taken prior to study administration (e.g. answer to the question of “Was the medication taken prior to study administration?” in CRF is not Yes). In this case, use the date of injection.
- If Day, Month and Year are all missing, the date will not be imputed, but the medication will be treated as though it began prior to the injection for purposes of determining status as prior or concomitant. If the medication is known to be not taken prior to study administration (e.g. answer to the question of “Was the medication taken prior to study administration?” in CRF is No), the medication will be treated as though it began after the injection for purposes of determining status as prior or concomitant.

2. Missing or partial medication stop date:

- If only Day is missing, use the earliest date of (last day of the month, study completion, discontinuation from the study, or death).
- If Day and Month are both missing, use the earliest date of (last day of the year, study completion, discontinuation from the study, or death).
- If Day, Month and Year are all missing, the date will not be imputed, but the medication will be flagged as a continuing medication.

#### **9.4. Appendix D Imputation Rules for Missing AE dates**

Imputation rules for missing or partial AE start dates and stop dates are defined below:

1. Missing or partial AE start date:

- If only Day is missing, use the first day of the month, unless:
  - The AE end date is after the date of injection or is missing AND the start month and year of the AE coincide with the start month and year of injection. In this case, use the date and time of injection, even if AE start time is collected.
- If Day and Month are both missing, use the first day of the year, unless:
  - The AE end date is after the date of injection or is missing AND the start year of the AE coincides with the start year of injection. In this case, use the date and time of injection, when time is available.
- If Day, Month and Year are all missing, the date will not be imputed. However, if the AE end date is prior to the date of injection, then the AE will be considered a pre-treatment AE. Otherwise, the AE will be considered to occur after exposure to study vaccination.

2. Missing or partial AE end dates will not be imputed.

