8.4.1. Time Period and Frequency for Collecting AE and SAE Information

All SAEs will be collected from the signing of ICF until the last day of study participation at the timepoints specified in the SoA ([Table 1](#)).

All, AESIs, MAAEs, and AEs leading to withdrawal from the study will be collected from the start of study intervention until the last day of study participation at the timepoints specified in the SoA ([Table 1](#)).

All other (unsolicited) AEs will be collected from the time of the administration of study vaccination through 28 days (the day of study vaccination and the subsequent 27 days) (see the SoA [[Table 1](#)]).

Solicited ARs will be collected during the solicited period, for 7 days (the day of study vaccination and the subsequent 6 days).

Non-serious medical occurrences that begin before the start of study intervention but after obtaining informed consent will be recorded as medical history/current medical conditions, not as AEs; however, if the condition worsens at any time during the study, it will be recorded and reported as an AE.

All SAEs will be recorded and reported to the Sponsor or designee immediately and under no circumstance should this exceed 24 hours, as indicated in [Section 10.3.5](#). The Investigator will submit any updated SAE data to the Sponsor within 24 hours of it being available.

Investigators are not obligated to actively seek information on AEs or SAEs after conclusion of the study participation. However, if the Investigator learns of any SAE at any time after a participant has been discharged from the study, and the Investigator considers the event to be

reasonably related to the study intervention or study participation, the Investigator must promptly notify the Sponsor.

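### SAP Appendix D classes an AE with a partial start date as pre-vaccination if it ended on the injection day, and leaves the class open if its end date is partial and confined to the injection month or year.

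*SAP*

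**What the plan says.** SAP 9.4 (Appendix D) has three branches for an incomplete AE start date.

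- **Day missing.** The default is the first of the month: "If only Day is missing, use the first day of the month, unless" an exception applies. The exception is "The AE end date is after the date of injection or is missing AND the start month and year of the AE coincide" with the month and year of injection. The AE then takes the injection date.
- **Day and month missing.** The default is 1 January of the start year. The exception has the same end-date test, with the year in place of month and year.
- **Whole date missing.** Nothing is imputed, but the AE is classed: "if the AE end date is prior to the date of injection, then the AE will be considered a pre-treatment AE". For every other case: "Otherwise, the AE will be considered to occur after exposure to study vaccination".

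On end dates, item 2 of the appendix says: "Missing or partial AE end dates will not be imputed". Appendix C, for medications, uses the same end-date test but does complete partial stop dates, taking the last day of the month or year or an earlier study exit.

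Protocol 8.4.1 sets what reaches the AE record. For unsolicited events: "All other (unsolicited) AEs will be collected from the time of the administration of study vaccination through 28 days". For earlier ones: "Non-serious medical occurrences that begin before the start of study intervention but after obtaining informed consent will be recorded as medical history/current medical conditions". SAEs are the exception, being collected from consent.

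**The concern.** The SAP 6.3.1 summaries take AEs that are new, or that worsen, after vaccination. For a new event with an incomplete start date, the Appendix D class therefore decides whether it is counted. Unsolicited AEs through 28 days, MAAEs and AESIs are primary endpoints.

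Two kinds of record are exposed when the known part of the start date matches injection:

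1. The end date is the injection day. It is neither after injection nor missing, so the default applies.
2. The end date is partial and cannot be ordered against injection. Whether it counts as missing is left to the programmer.

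If a truly post-dose event is caught, the error can only remove it from the tables. SAP Section 1 lets the SAP prevail over the protocol where methods differ, so protocol 8.4.1 does not correct the rule by itself.

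**Working it through.** No published figure needs reproducing; this is a check of a date rule.

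**Step 1. Run the day-missing branch on examples.** Assume injection on 15 June 2023.

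| Recorded start | Recorded end | Imputed start | Class |
|---|---|---|---|
| June, day unknown | 16 June or later | 15 June | post |
| June, day unknown | missing | 15 June | post |
| June, day unknown | 15 June | 1 June | **pre** |
| June, day unknown | June, day unknown | 15 June if partial counts as missing; 1 June if not | **undetermined** |
| June, day unknown | July, day unknown | 15 June | post |
| July, day unknown | any later or partial July date | 1 July | post |

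The fifth row is safe because any day in July is after 15 June. The last is safe because the default date is itself after injection.

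**Step 2. How often the injection-day case goes wrong.** Taking every day of 2023 as the injection date, an AE with a month-only start that ends on the injection day is placed before vaccination for 365 − 12 = 353 dates. The 12 that escape are the firsts of the months. With a year-only start, only 1 January escapes, so 365 − 1 = 364 dates are affected.

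**Step 3. Compare with the third branch.** Take the same AE, ending on 15 June, with no start date at all. Its end is not before injection, so it is post-vaccination. The same holds for an end of June, day unknown, which is not known to precede injection. Learning that the AE started in June can therefore turn a counted event into an uncounted one, although June also contains the injection date.

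**Step 4. Compare with protocol 8.4.1.** A non-serious event that began between consent and dosing belongs in medical history. A non-serious entry on the AE record is thus presumptively post-dose, or a worsening. Defaulting it to before the dose reverses that presumption.

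**Step 5. Size of the ambiguous case.** Assume injection on each day of 2023, onset spread evenly over Days 1 to 28, and both start and end recorded as month only. Share of these post-dose AEs moved to before vaccination:

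| AE duration | Partial does not count as missing | Partial counts as missing |
|---|---|---|
| 1 day | 52% | 0% |
| 3 days | 46% | 0% |
| 7 days | 34% | 0% |
| 14 days | 17% | 0% |

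These are shares of AEs with both days unknown, not of all AEs. The documents do not say how many such AEs there are.

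**Step 6. Weight of one participant.** The arms have 60 or 30 participants (protocol Table 4): 1/60 = 1.7 percentage points and 1/30 = 3.3 percentage points.

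**The case against.** A reader might infer that any partial end date sends an AE to before vaccination and out of the primary safety tables. The documents do not support that:

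- A partial end date in a later month is known to be after injection, and a start month after the injection month stays post-dose.
- Solicited reactions follow Appendix I.
- AEs that worsen after vaccination are still summarised.
- Even for the same-month partial end, excluding the AE is only one reading. Appendix D's title speaks of missing dates yet covers partial ones, and a partial end date that is not imputed offers no complete date to compare. Reading it as missing is natural, and then nothing is lost.

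The definite case should also be rare. A post-dose AE that ended on the injection day started that day too, so the site would have to know the end day but not the start day. Day 1 is an observed clinic visit with a blood draw at 6 hours. Nor is every AE record post-dose: SAEs are collected from consent, and the Schedule of Activities records unsolicited AEs from the day of intervention, which could admit an event from earlier that day.

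Appendix D does not push in one direction overall. Its exception can assign a pre-dose onset to the injection date. The first-of-month default can also pull a late event into the 28-day period: with injection on 15 May, an onset on 20 June (Day 37) recorded only as June becomes 1 June, Day 18.

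All of this stands, and it limits the size of the point. It does not explain why an injection-day ending is pre-dose in two branches and post-dose in the third, nor tell the programmer how to order a same-month partial end. Appendix C shows that the second gap is real, since there the same test comes with a rule that completes the stop date. The AE listings planned in SAP 6.3.1.1 would keep records visible but would not restore them to the counts.

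**Conclusion.** The point holds in a narrow form. For a start that is partial and matches the injection month or year, an injection-day ending is classed as pre-vaccination by the text itself, except when injection fell on the default date. For an end date that is partial and confined to the injection month, or gives only the injection year, the text allows either class. The pre-vaccination class conflicts in both cases with the third branch of the same appendix and, for non-serious AEs, with protocol 8.4.1.

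The injection-day result needs no assumption beyond the wording. The 17% to 52% range rests on the assumptions in Step 5 and on the adverse reading; under the other reading it is 0%. The number of affected records is not in the documents and is probably small. No hypothesis is tested, so what is at stake is the accuracy of descriptive rates for primary endpoints, in arms where one participant is worth 1.7 or 3.3 percentage points. The change is worth making because it is cheap and removes a programmer's choice from a primary safety classification.

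**What to change.** In both partial-start branches of SAP Appendix D, replace the exception with:

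*If the start month and year (or start year) coincide with those of injection, use the date of injection, unless the AE end date, complete or partial, shows that the AE ended before the date of injection.*

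This settles the injection-day ending and the unorderable partial end together, and gives the first two branches the logic of the third. End dates still need no imputation.

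The cost is two sentences in the SAP and about one line of code. The downside is that a rare pre-dose SAE with partial dates may be counted as post-dose, which errs toward over-counting harm.
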